**2. using the measurement of hemoglobin.**

Pads		
1 point	For each lightly stained pad	
5 points	For each moderately stained pad	
20 points	For each completely saturated pad	
Tampons		
1 point	For each lightly stained tampon	
5 points	For each moderately stained tampon	
10 points	For each completely saturated tampon	
Clots/Flooding		
1 point	For each small clot	
5 points	For each large clot	
5 points	For each episode of flooding	

  

Parameter	Normal	Abnormal	
Frequency	Absent (no bleeding) = amenorrhea		
	Infrequent (>38 days)		
	Normal (≥24 to ≤38 days)		
	Frequent (<24 days)		
Duration	Normal (≤8 days)		
	Prolonged (>8 days)		
Regularity	Normal or "Regular" (shortest to longest cycle variation: ≤7-9 days)*		
	Irregular (shortest to longest cycle variation: ≥8-10 days)*		
Flow Volume (patient determined)	Light		
	Normal		
	Heavy		
Intermenstrual Bleeding (IMB) Bleeding between cyclically regular onset of menses	None		
	Random		
	Cyclic (Predictable)	Early Cycle	
		Mid Cycle	
		Late Cycle	
Unscheduled Bleeding on Progestin ± Estrogen  Gonadal Steroids (birth control pills, rings, patches or injections)	Not Applicable (not on gonadal steroid medication)		
	None (on gonadal steroid medication)		
	Present		

**FIGURE 2** The FIGO AUB System (*Munro et al., 2018*)

**Table 1: Comparison between two groups regarding demographic data of patients:**

		Group A (Dienogest) (N=20)			Group B (NAC) (N=20)			t*	P value
		Range	Mean	SD	Range	Mean	SD		
Age		23.00-45.00	40.30	6.48	23.00-45.00	38.20	6.57	1.02	0.32
		N		%		N		%	
Residence	Urban	15	75.0%		14	70.0%		0.13	0.72

	Rural	5	25.0%	6	30.0%		
Occupation	Housewife	19	95.0%	19	95.0%	0.00 FE	1.00
	Working	1	5.0%	1	5.0%		

\*Student t test

\*\*Chi square test (FE: Fisher Exact)

Both groups have similar age distributions, with no significant difference (p = 0.32).

The distribution of patients based on residence and occupation is also similar between the groups (P value >0.05), indicating well-matched cohorts for demographic factors.

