### **Study procedures and interventions:**

1. After approval of study protocol, women will be enrolled into the study according to inclusion and exclusion criteria.
2. Eligible patients will be randomized using a computer-generated sequence 1:1 either to
3. **Intervention:**
  - Group (A): women will receive Dienogest, with brand name GYNOPROGEST, 2mg pills daily for 3 months (20 cases) (*Ichigo et al., 2011*)
  - Group (B): women will receive NAC, with brand name GEMACYSTINE, orally at a dose of 600 mg/day for 3 months ( 20 cases) (*Aghaamoo et al., 2021*)
4. **Methodology:** All cases will be subjected to:
  - **Full history taking:** with special emphasis to age, parity, BMI, age of menarche, obstetric history, drug history as well as presence of any medical disease.
  - **Full general examination:** for pallor, fatigue.
  - **Abdominal examination:** to assess the leiomyoma size, surface, contour and consistency.
  - **Bimanual vaginal examination(for uterus <12 weeks):** to confirm its uterine origin.
  - **Vaginal Ultrasound examination with the addition of a transabdominal approach if needed** to diagnose and assess the leiomyoma (size and number).

Ultrasound will be done using the same machine.

The principal investigator will hold regular meetings with the research team to assess data and adverse events.

Serious adverse events will be reported to the research ethics committee, Faculty of medicine, Ain Shams university within 24 hours.

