**Table 2: Comparison between two groups regarding medical history of patients:**

		Group A (Dienogest) (N=20)		Group B (NAC) (N=20)		X  *	P value
		N	%	N	%		
Special habits	No	20	100.0%	20	100.0%	-	-
Past history of gynecologic cancer	No	20	100.0%	20	100.0%	-	-
Past history of pelvic infection	No	20	100.0%	20	100.0%	-	-

Medical history	Negative	20	100.0%	20	100.0%	-	-
Surgical history	Negative	12	60.0%	7	35.0%	2.51	0.11
	Positive	8	40.0%	13	65.0%		

\*Chi square test

There are no significant differences between the groups in terms of special habits, history of gynecologic cancer, pelvic infection, or medical history.

A notable but non-significant trend is observed in the surgical history, where Group B has a higher percentage of positive surgical history (65% vs. 40%), though this difference is not statistically significant ( $p = 0.11$ ).

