**Table 5: Comparison between two groups regarding anthropometric measures of patients:**

	Group A (Dienogest) (N=20)			Group B (NAC) (N=20)			t*	P value
	Range	Mean	SD	Range	Mean	SD		
Weight (Kg)	60.00-120.00	78.70	15.04	60.00-95.00	81.20	9.34	0.63	0.53
Height (cm)	158.00-173.00	164.90	4.64	158.00-172.00	166.75	4.46	1.29	0.21
BMI (Kg/m  )	22.77-46.87	28.98	5.86	24.03-32.11	29.14	2.54	0.11	0.91

\*Student t test

There are no significant differences in weight, height, or BMI between the two groups (P value>0.05), indicating that both groups are comparable in terms of anthropometric measures.

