**Table 6: Comparison between two groups regarding clinical examination of patients:**

	Group A (Dienogest) (N=20)			Group B (NAC) (N=20)			t*	P value
	Range	Mean	SD	Range	Mean	SD		
Temperature	37.00-37.00	37.00	0.00	37.00-37.00	37.00	.00	-	-
Pulse	65.00-85.00	76.90	6.04	73.00-88.00	80.65	3.95	2.32	0.03
Systolic BP	90.00-120.00	110.50	9.45	90.00-120.00	106.00	8.83	1.56	0.13

Diastolic BP		60.00-80.00	72.00	8.34	60.00-80.00	67.00	8.65	1.86	0.07		
		N	%		N	%		$\chi^2$ **	P value		
General appearance	Normal	20	100.0%		20	100.0%		-	-		
Pallor	No	19	95.0%		20	100.0%		1.03 FE	1.00		
	Yes	1	5.0%		0	0.0%					
Abdominal obstetric examination	Free	20	100.0%		19	95.0%		1.03 FE	1.00		
	Distended abdomen	0	0.0%		1	5.0%					
local examination	Free	16	80.0%		11	55.0%		3.69 FE	0.22		
	Vaginal bleeding	2	10.0%		7	35.0%					
	Bulky uterus	2	10.0%		2	10.0%					

\*Student t test

\*\*Chi square test (FE: Fisher Exact)

The only significant difference observed is in the pulse rate, with Group B having a slightly higher mean pulse rate ( $p = 0.03$ ). Other clinical parameters like temperature, systolic, and diastolic blood pressure do not differ significantly between the groups ( $P$  value  $>0.05$ ).

[figure not shown]

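### Similarity of the arms is inferred from non-significant baseline tests, which 20 women per arm cannot support, and baseline differences on outcome-related variables go unadjusted

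*SAP*

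**What the plan says.** The protocol (Study procedures and interventions) states: "Eligible patients will be randomized using a computer-generated sequence 1:1". The SAP tables show 20 women in each arm. Tables 1 to 6 compare the arms at baseline with Student t, chi-square or Fisher exact tests and draw conclusions in the text beneath:

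- **Table 1.** Residence and occupation have a distribution that "is also similar between the groups (P value >0.05), indicating well-matched cohorts for demographic factors". Age is called similar on P = 0.32.
- **Table 5.** Weight, height and BMI all have P above 0.05, "indicating that both groups are comparable in terms of anthropometric measures".
- **Table 6.** "The only significant difference observed is in the pulse rate, with Group B having a slightly higher mean pulse rate". Vaginal bleeding at local examination (2/20 on dienogest, 7/20 on NAC) is not mentioned. It sits in a three-level row with P = 0.22.
- **Table 4.** The text says gravidity, parity and abortions are similarly distributed, with nothing significant. The table prints P = 0.03 for the number of abortions.
- **Table 2.** The text does remark on surgical history (65% v 40%, P = 0.11), so the SAP is not silent on every non-significant difference.

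Tables 9 and 10 compare post-treatment PBAC and hemoglobin between arms without adjustment for the baseline value. No standardised difference or confidence interval appears in the tables.

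**The concern.** A non-significant test is not evidence of similarity. Its result depends on sample size as well as on the difference, and at 20 v 20 quite large differences pass. Under sound randomisation each baseline test gives P above 0.05 about 95% of the time, so that result says little about how alike these two particular samples are.

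Two things are at stake. Readers are told that arms are alike on grounds that cannot show it. And where the samples did differ on something tied to an outcome, such as bleeding or hemoglobin, the post-treatment comparison takes no account of it.

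**Working it through.** **Inputs.** n = 20 per arm (SAP table headings). Threshold 0.05, taken as two-sided because that reproduces the printed P values. Means, SDs and counts are from SAP Tables 1, 4, 5, 6, 10, 11 and 12.

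**1. Reproduce the SAP's own test (age, Table 1).** Pooled SD = √((6.48² + 6.57²)/2) = 6.53. Standardised difference = (40.30 − 38.20)/6.53 = 0.32. t = 0.32/√(2/20) = 1.02, P = 0.32, as printed.

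**2. Smallest observed difference the test can flag.** t(0.975, 38 df) × √(2/20) = 2.024 × 0.316 = **0.64 SD**. An observed difference of 0.5 SD gives t = 0.5/0.316 = 1.58, **P = 0.12**.

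**3. Tables with an explicit similarity claim.**
- Largest mean differences: age 0.32 SD (Table 1); height 1.85/4.55 = 0.41 SD (Table 5).
- Mean BMI is almost equal: 28.98 v 29.14, or 0.04 SD.
- Spread is not. BMI SD ratio = 5.86/2.54 = 2.3 (ranges 22.77–46.87 v 24.03–32.11). Weight SD ratio = 15.04/9.34 = 1.6. A t test compares means only.

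**4. Outcome-related differences elsewhere.**
- Vaginal bleeding at examination (Table 6): 0.10 v 0.35. Standardised difference = 0.25/√((0.10×0.90 + 0.35×0.65)/2) = 0.25/0.398 = **0.63**.
- Baseline hemoglobin (Table 10): pooled SD = √((1.65² + 1.46²)/2) = 1.56. Standardised difference = 0.85/1.56 = **0.55**, t = 1.73, P = 0.09, as printed.

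**5. Table 4 against its text.** Abortions 0/1/2/3/5: 13/4/3/0/0 v 8/7/0/4/1, printed P = 0.03. Collapsed to any v none: 7/20 v 12/20, printed P = 0.11. The text does not fit the first of these.

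**6. What adjustment can do: hemoglobin.** This is an approximation from rounded summary figures.
- Unadjusted post-treatment difference, dienogest − NAC = 10.99 − 11.63 = −0.64. SE = √((1.41² + 1.51²)/20) = 0.46, so t = 1.39 as printed, 95% CI −1.58 to 0.30.
- Variance of change from the paired t tests, 20 × (mean change/t)²: dienogest 20 × (0.45/2.78)² = 0.52; NAC 20 × (0.24/1.40)² = 0.59.
- Before–after covariance, (variance before + variance after − variance of change)/2: 2.09 and 1.91.
- Pooled slope = (2.09 + 1.91)/(1.65² + 1.46²) = 0.83.
- Adjusted difference = −0.64 − 0.825 × (−0.85) = **+0.06**. Residual variance = 19 × (1.41² + 1.51² − 0.825 × 4.005)/37 = 0.49. SE = √(0.49 × (2/20 + 0.85²/(19 × 4.85))) = 0.23, 95% CI about −0.41 to 0.53.

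The SAP's conclusion of no significant difference stands, but the estimate moves from −0.64 to about zero and its standard error halves. PBAC cannot be reworked this way, because only medians, IQRs and rank statistics are given.

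**The case against.** **The claims are scoped.** Table 1 speaks of demographic factors and Table 5 of anthropometric measures. The SAP does not call the arms comparable overall. Within those tables the mean differences are modest, and only the spread of BMI and weight tells against the wording. The Table 6 sentence about pulse is true of the P values in that table. This stands: a reader might infer that the printed figures refute the two claims outright, and they do not. What fails is the step from P above 0.05 to similarity.

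**A power argument would be misplaced.** A reader might say these tests miss a 0.5-SD imbalance about two times in three, since power at 20 per arm is 34%. That figure is for a true population difference, which randomisation makes zero. Imbalance is a property of the sample, and an observed 0.5-SD imbalance is never flagged.

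**Chance imbalance is expected.** Under sound randomisation, an observed difference above 0.5 SD arises in about 12% of independent variables at this size. A reader might suspect failed randomisation; these figures do not support that. Unadjusted comparison also remains valid in a randomised trial.

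**The results may well hold.** Table 9 gives Z = 4.10 for post-treatment PBAC. Dienogest had the higher baseline median (70 v 50), so adjustment for baseline PBAC could strengthen its advantage. The bleeding sign points the other way. A reader might infer that the PBAC result would reverse; nothing in the documents shows this.

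What remains is that the similarity wording is unsupported, the Table 4 sentence conflicts with its table, and adjustment for the baseline outcome costs almost nothing.

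**Conclusion.** The point holds as one of inference and reporting, with a modest consequence for analysis. At 20 per arm, P above 0.05 means only that an observed mean difference is below 0.64 SD, and it says nothing about spread. That cannot support the wording under Tables 1 and 5. Reliance on significance also leaves uncommented a 25-point difference in bleeding at examination (0.63) and a 0.55-SD difference in baseline hemoglobin, itself a secondary outcome. The Table 4 text is at odds with its own P = 0.03.

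This rests on a two-sided 0.05 threshold and, for the bleeding sign, on the Table 6 examination having been at enrolment; the SAP table does not date it. The hemoglobin reconstruction also assumes a common slope in both arms.

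**What to change.** 1. **Baseline tables.** Remove the test statistics and P values. Report the observed difference or standardised difference for each row. Replace the similarity wording under Tables 1 and 5 with a factual description that includes the unequal spread of BMI and weight. Correct the Table 4 sentence on abortions. Do not add a statement that imbalances of 0.5 SD or more cannot be excluded, because the imbalances in the measured variables are known from the sample.
2. **Outcome comparisons.** Beside Tables 9 and 10, compare the arms after treatment with adjustment for the baseline value of the same outcome: rank-based ANCOVA or a proportional-odds model for PBAC, and ANCOVA for hemoglobin. Label these post hoc and state whether the conclusions hold.
3. **Optional.** Add vaginal bleeding at examination to the PBAC model as a further sensitivity analysis, if that examination was at enrolment. Say that the covariate was chosen after seeing the data.

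**Cost.** Rewording and two models on data already collected, with no new patients or procedures. The baseline statement becomes less favourable, and the added models carry the limits of post hoc work.

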**Table 2: Comparison between two groups regarding medical history of patients:**

		Group A (Dienogest) (N=20)		Group B (NAC) (N=20)		X  *	P value
		N	%	N	%		
Special habits	No	20	100.0%	20	100.0%	-	-
Past history of gynecologic cancer	No	20	100.0%	20	100.0%	-	-
Past history of pelvic infection	No	20	100.0%	20	100.0%	-	-

Medical history	Negative	20	100.0%	20	100.0%	-	-
Surgical history	Negative	12	60.0%	7	35.0%	2.51	0.11
	Positive	8	40.0%	13	65.0%		

\*Chi square test

There are no significant differences between the groups in terms of special habits, history of gynecologic cancer, pelvic infection, or medical history.

A notable but non-significant trend is observed in the surgical history, where Group B has a higher percentage of positive surgical history (65% vs. 40%), though this difference is not statistically significant ( $p = 0.11$ ).

**Table 3: Comparison between two groups regarding Gynecological history of patients:**

		Group A (Dienogest) (N=20)		Group B (NAC) (N=20)		$X^2^*$	P value
		N	%	N	%		
Regularity of cycle	Regular	12	60.0%	10	50.0%	0.40	0.53
	Irregular	8	40.0%	10	50.0%		
Contraceptive methods	No	8	40.0%	7	35.0%	2.15	0.67

	IUD	10	50.0%	10	50.0%	FE	
	OCP	2	10.0%	1	5.0%		
	Tubal ligation	0	0.0%	2	10.0%		
Previous complications from contraceptive method	No	20	100.0%	20	100.0%	-	-

\*Chi square test (FE: Fisher Exact)

Both groups show a similar distribution in terms of cycle regularity and contraceptive methods.

The use of contraceptive methods like IUDs is equally common in both groups (50%), suggesting similar baseline characteristics for contraceptive use.

**Table 4: Comparison between two groups regarding obstetric history of patients:**

	Group A (Dienogest) (N=20)			Group B (NAC) (N=20)			t*	P value
	Range	Mean	SD	Range	Mean	SD		
Duration since last delivery (years)	3.50-25.00	11.88	5.38	2.50-20.00	9.73	6.09	1.06	0.30
	N	%		N	%		X  **	P value
Gravidity	0	3	15.0%	1	5.0%	8.75	0.47	

	1	2	10.0%	3	15.0%	FE	
	2	5	25.0%	3	15.0%		
	3	3	15.0%	6	30.0%		
	4	3	15.0%	2	10.0%		
	5	2	10.0%	1	5.0%		
	6	1	5.0%	0	0.0%		
	7	1	5.0%	0	0.0%		
	8	0	0.0%	3	15.0%		
	9	0	0.0%	1	5.0%		
Gravidity	0	3	15.0%	1	5.0%	1.16 FE	0.73
	1-3	10	50.0%	12	60.0%		
	4 or more	7	35.0%	7	35.0%		
Parity	0	3	15.0%	5	25.0%	5.79 FE	0.47
	1	2	10.0%	2	10.0%		
	2	8	40.0%	3	15.0%		
	3	4	20.0%	5	25.0%		
	4	0	0.0%	2	10.0%		
	5	3	15.0%	2	10.0%		
	7	0	0.0%	1	5.0%		
Parity	0	3	15.0%	5	25.0%	5.79 FE	0.47
	1-3	14	70.0%	10	50.0%		
	4 or more	3	15.0%	5	25.0%		
Abortions	0	13	65.0%	8	40.0%	9.21 FE	0.03
	1	4	20.0%	7	35.0%		
	2	3	15.0%	0	0.0%		
	3	0	0.0%	4	20.0%		
	5	0	0.0%	1	5.0%		
Abortions	No	13	65.0%	8	40.0%	2.51	0.11

	Yes	7	35.0%	12	60.0%		
Living	0	3	15.0%	5	25.0%	5.56 FE	0.56
	1	4	20.0%	2	10.0%		
	2	5	25.0%	3	15.0%		
	3	6	30.0%	5	25.0%		
	4	1	5.0%	4	20.0%		
	5	1	5.0%	0	0.0%		
	7	0	0.0%	1	5.0%		
Living	0	3	15.0%	5	25.0%	2.70 FE	0.29
	1-3	15	75.0%	10	50.0%		
	4 or more	2	10.0%	5	25.0%		
Mode of delivery (years)	NVD	7	41.2%	5	33.3%	0.21	0.65
	CS	10	58.8%	10	66.7%		

\*Student t test

\*\*Chi square test (FE: Fisher Exact)

The gravidity, parity, and history of abortions are distributed similarly across both groups, with no significant differences noted.

Group A shows a slightly higher mean duration since the last delivery compared to Group B, but this difference is not statistically significant ( $p = 0.30$ ).

**Table 5: Comparison between two groups regarding anthropometric measures of patients:**

	Group A (Dienogest) (N=20)			Group B (NAC) (N=20)			t*	P value
	Range	Mean	SD	Range	Mean	SD		
Weight (Kg)	60.00-120.00	78.70	15.04	60.00-95.00	81.20	9.34	0.63	0.53
Height (cm)	158.00-173.00	164.90	4.64	158.00-172.00	166.75	4.46	1.29	0.21
BMI (Kg/m  )	22.77-46.87	28.98	5.86	24.03-32.11	29.14	2.54	0.11	0.91

\*Student t test

There are no significant differences in weight, height, or BMI between the two groups (P value>0.05), indicating that both groups are comparable in terms of anthropometric measures.

**Table 6: Comparison between two groups regarding clinical examination of patients:**

	Group A (Dienogest) (N=20)			Group B (NAC) (N=20)			t*	P value
	Range	Mean	SD	Range	Mean	SD		
Temperature	37.00-37.00	37.00	0.00	37.00-37.00	37.00	.00	-	-
Pulse	65.00-85.00	76.90	6.04	73.00-88.00	80.65	3.95	2.32	0.03
Systolic BP	90.00-120.00	110.50	9.45	90.00-120.00	106.00	8.83	1.56	0.13

Diastolic BP		60.00-80.00	72.00	8.34	60.00-80.00	67.00	8.65	1.86	0.07		
		N	%		N	%		$\chi^2$ **	P value		
General appearance	Normal	20	100.0%		20	100.0%		-	-		
Pallor	No	19	95.0%		20	100.0%		1.03 FE	1.00		
	Yes	1	5.0%		0	0.0%					
Abdominal obstetric examination	Free	20	100.0%		19	95.0%		1.03 FE	1.00		
	Distended abdomen	0	0.0%		1	5.0%					
local examination	Free	16	80.0%		11	55.0%		3.69 FE	0.22		
	Vaginal bleeding	2	10.0%		7	35.0%					
	Bulky uterus	2	10.0%		2	10.0%					

\*Student t test

\*\*Chi square test (FE: Fisher Exact)

The only significant difference observed is in the pulse rate, with Group B having a slightly higher mean pulse rate ( $p = 0.03$ ). Other clinical parameters like temperature, systolic, and diastolic blood pressure do not differ significantly between the groups ( $P$  value  $>0.05$ ).

[figure not shown]
**Table 7: Comparison between two groups regarding volume of leiomyoma before and after treatment (largest lesion):**

[figure not shown]
	Group A (Dienogest) (N=20)			Group B (NAC) (N=20)			Z*	P value
	Range	Median	IQR	Range	Median	IQR		
Leiomyoma volume (cm  ) before	1.43-45.24	15.53	4.31-25.01	1.00-108.00	9.00	4.09-14.32	0.52	0.61

Leiomyoma volume (cm  ) after	2.66-76.36	19.54	8.25-32.61	3.24-115.90	13.13	7.74-24.16	0.50	0.63
---	------------	-------	------------	-------------	-------	------------	------	------

\*Mann Whitney U test

Median leiomyoma volume slightly increases after treatment in both groups, but the differences between the groups are not statistically significant ( $p > 0.05$ ), indicating that both treatments had similar effects on leiomyoma volume.

[figure not shown]

[figure not shown]

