## 2.AIM / OBJECTIVES

This study aims to assess the effect of Dienogest and NAC on the volume of uterine leiomyoma in women previously diagnosed with leiomyoma.

**Research hypothesis:** In women with leiomyoma, the use of NAC as a non-hormonal drug in the treatment of leiomyoma of the uterus is more feasible and effective in the reduction of leiomyoma volume with no hormonal side effects compared with Dienogest.

**Research question:** In women with leiomyoma, is the use of NAC as a non-hormonal drug in the treatment of leiomyoma of the uterus more feasible and effective in the reduction of leiomyoma volume with no hormonal side effects compared with Dienogest?

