### **Sample size Justification:**

Assuming an effect size of 1.0 reflecting the percentage change (reduction) in the volume of uterine leiomyoma, a sample of 12 patients in each group will be enough to detect such rate, if true, at 0.01  $\alpha$  error and 0.90 power of the test. We will increase the sample to 20 cases in each group to maximize the power of the study.

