**Table 8: Comparison between two groups regarding dysmenorrhea VAS score before and after treatment:**

	Group A (Dienogest) (N=20)			Group B (NAC) (N=20)			t*	P value
	Range	Mean	SD	Range	Mean	SD		
VAS score for dysmenorrhea before	2.00-10.00	7.10	2.88	5.00-10.00	7.30	1.78	0.26	0.79
VAS score for dysmenorrhea after	.00-8.00	1.35	2.35	1.00-7.00	3.70	1.69	3.64	0.001

\*Student t test

A significant reduction in VAS scores for dysmenorrhea is observed in both groups after treatment, with Group A showing a more pronounced improvement ( $p = 0.001$ ).

[figure not shown]

[figure not shown]

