**Table 10: Comparison between two groups regarding hemoglobin level before and after treatment:**

	Group A (Dienogest) (N=20)			Group B (NAC) (N=20)			t*	P value
	Range	Mean	SD	Range	Mean	SD		
Hemoglobin level before	7.60-12.80	10.54	1.65	9.30-13.60	11.39	1.46	1.73	0.09
Hemoglobin level after	8.20-13.20	10.99	1.41	7.90-13.80	11.63	1.51	1.39	0.17

\*Student t test

While hemoglobin levels increase slightly in both groups after treatment, the differences between the groups are not statistically significant ( $p > 0.05$ ).

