**Comparison of outcome measures before and after treatment:**

**Table 11: Comparison between outcome measures before and after treatment in group A (Dienogest):**

	Mean	SD	t*	P value
VAS score for dysmenorrhea before	7.10	2.88	7.74	0.00
VAS score for dysmenorrhea after	1.35	2.35		
Hemoglobin level before	10.54	1.65	2.78	0.01
Hemoglobin level after	10.99	1.41		
	Median	IQR	Z**	P value
Leiomyoma volume (cm3) before	15.53	4.31-25.01	2.78	0.01
Leiomyoma volume (cm3) after	19.54	8.25-32.61		
HMB assessment (PBAC) before	70.00	15.00-110.00	2.88	0.004
HMB assessment (PBAC) after	0.00	0.00-8.50		

\*Paired-samples t test    \*\* Wilcoxon Signed Ranks Test

Significant improvements are observed in VAS scores, HMB assessment, and hemoglobin levels after treatment, suggesting that Dienogest is effective. But leiomyoma volume is significantly increased after treatment.

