**Table 12: Comparison between outcome measures before and after treatment in group B (NAC):**

	Mean	SD	t*	P value
VAS score for dysmenorrhea before	7.30	1.78	6.49	0.00
VAS score for dysmenorrhea after	3.70	1.69		
Hemoglobin level before	11.39	1.46	1.40	0.18
Hemoglobin level after	11.63	1.51		
	Median	IQR	Z**	P value
Leiomyoma volume (cm3) before	9.00	4.09-14.32	3.46	0.001
Leiomyoma volume (cm3) after	13.13	7.74-24.16		
HMB assessment (PBAC) before	50.00	15.00-90.00	1.78	0.08
HMB assessment (PBAC) after	25.00	15.00-70.00		

\*Paired-samples t test    \*\* Wilcoxon Signed Ranks Test

Similar to Group A, Group B also shows significant improvements in VAS scores and increase in leiomyoma volume, though the changes in hemoglobin levels and HMB assessments are less pronounced.

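### The trial is sized on percentage change in leiomyoma volume, but the arms are compared only on raw volumes, and similar effects are inferred from a non-significant P value

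*SAP*

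**What the plan says.** - **Sizing.** The protocol's Sample size Justification begins "Assuming an effect size of 1.0 reflecting the percentage change (reduction) in the volume of uterine leiomyoma". It sets alpha at 0.01 and power at 0.90, and raises the sample to 20 per group.
- **Question.** Protocol section 2 (Aim / Objectives) asks whether NAC is "more feasible and effective in the reduction of leiomyoma volume with no hormonal side effects compared with Dienogest". This is a superiority question about reduction. No equivalence margin is stated.
- **Outcome.** The protocol's Outcomes section names leiomyoma volume as primary, measured at baseline and again after 3 months. It gives no change measure and no test.
- **Between-arm analysis.** SAP Table 7 reports two separate Mann-Whitney tests on raw volume, before (Z = 0.52, P = 0.61) and after (Z = 0.50, P = 0.63). The text beneath says the arms do not differ significantly, "indicating that both treatments had similar effects on leiomyoma volume".
- **Within-arm analysis.** Baseline and 3-month values are paired only inside each arm. Table 11 (dienogest) states, "But leiomyoma volume is significantly increased after treatment". Table 12 (NAC) states, "Group B also shows significant improvements in VAS scores and increase in leiomyoma volume".
- **Secondary outcomes.** Tables 8 to 10 follow the Table 7 layout. Table 8 attaches P = 0.001 to a statement about improvement, "with Group A showing a more pronounced improvement", although that P value comes from the comparison of final scores.

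**The concern.** There are two separate problems.

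1. **The quantity tested is not the quantity planned.** A statement about the treatments' effects on volume needs a between-arm comparison of change, or of final volume adjusted for baseline. Two tests of level and two within-arm tests do not supply one. The unadjusted final-volume test keeps its type I error under randomisation, but it carries any chance baseline difference into the comparison and gives up whatever precision baseline could add.
2. **Non-significance is read as similarity.** With 20 women per arm, P > 0.05 is compatible with large differences in either direction, and no interval is given to show how large.

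At stake is the primary conclusion. On the available text, the trial has no estimate of how differently volume changed under the two drugs.

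**Working it through.** **Plan's own figures.** Two-sided normal P values for Z = 0.52 and 0.50 are 0.60 and 0.62, close to the printed 0.61 and 0.63. Table 7 is therefore what it appears to be: two tests of level.

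**Medians (Table 7).**
- Dienogest: 19.54/15.53 = 1.26, a rise of 4.01 cm³.
- NAC: 13.13/9.00 = 1.46, a rise of 4.13 cm³.
- NAC/dienogest ratio of medians: 9.00/15.53 = 0.58 before, 13.13/19.54 = 0.67 after.

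The relative rises differ and the absolute rises are almost equal. Changes of medians are not medians of individual change, so neither shows a difference or rules one out. They show only that Table 7 leaves the comparison of change open.

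**What a final-volume comparison can exclude.** Assumptions: log-normal volumes, 20 per arm, two-sided, post-treatment log-SD taken from the IQRs as ln(Q3/Q1)/1.349.
- Dienogest: ln(32.61/8.25)/1.349 = 1.019.
- NAC: ln(24.16/7.74)/1.349 = 0.844.
- Pooled: √[(1.019² + 0.844²)/2] = 0.935.

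SE of the log ratio = 0.935 × √(1 − r²) × √(2/20), where r is the pre-post correlation. The SAP does not report r for volume, so a range is shown; r = 0 stands for no adjustment. The interval is centred on an observed ratio of 1.0 and equals exp(±t × SE), with 38 df unadjusted and 37 adjusted. Power is Φ(|ln 0.7|/SE − z). The 30% difference is an illustration of mine and is not in the documents.

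| r | Variance removed (r²) | SE | 95% interval if observed ratio = 1.0 | Power, alpha 0.01 | Power, alpha 0.05 |
|---|---|---|---|---|---|
| unadjusted | – | 0.296 | 0.55–1.82 | 0.09 | 0.23 |
| 0.3 | 9% | 0.282 | 0.56–1.77 | 0.10 | 0.24 |
| 0.5 | 25% | 0.256 | 0.60–1.68 | 0.12 | 0.29 |
| 0.7 | 49% | 0.211 | 0.65–1.53 | 0.19 | 0.39 |
| 0.8 | 64% | 0.177 | 0.70–1.43 | 0.29 | 0.52 |
| 0.9 | 81% | 0.129 | 0.77–1.30 | 0.58 | 0.79 |

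**Hemoglobin, where r can be recovered (Tables 10 to 12).** SD of paired difference = |mean difference| × √20 / t.
- Dienogest: 0.45 × √20/2.78 = 0.724, so r = (1.65² + 1.41² − 0.724²)/(2 × 1.65 × 1.41) = 0.90.
- NAC: 0.24 × √20/1.40 = 0.767, so r = 0.87.
- Pooled within-arm slope: 0.825.
- Final-level difference, dienogest minus NAC: 10.99 − 11.63 = −0.64 g/dL (SE 0.46, 95% CI −1.58 to 0.30).
- Adjusted: −0.64 − 0.825 × (10.54 − 11.39) = +0.06 g/dL (SE 0.23, 95% CI −0.41 to 0.53, P = 0.79).

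The apparent deficit on dienogest is baseline imbalance, and adjustment halves the standard error. Table 10's statement of no significant difference is unchanged.

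**VAS (Tables 8, 11, 12).** The same steps give r = 0.21 and −0.02 and a pooled slope of 0.116. The adjusted difference is −2.33 (95% CI −3.64 to −1.01, P = 0.001). A direct test of change gives (−5.75) − (−3.60) = −2.15, SE 0.927, P = 0.026. PBAC cannot be recovered from the printed summaries.

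**The case against.** - **Table 7 matches the declared outcome.** The Outcomes section names volume itself, and a final-value comparison is valid under randomisation. Both points stand. The mismatch is with the sample-size basis and the question about reduction, and neither point makes P > 0.05 evidence of similarity.
- **Part of the SAP cannot be seen.** Its opening pages and the figures around Table 7 are not in the text reviewed, so a comparison of change could exist there. The finding is therefore limited to the visible text; the conclusion under Table 7 is printed and cites only p > 0.05.
- **The gain from adjustment depends on an unknown correlation.** True. At r = 0.3 to 0.5 it is small, and at alpha 0.01 even r = 0.9 gives power of only 0.58 for a 30% difference.
- **Log-normality is strained.** For dienogest at baseline the log-scale quartile gaps are 1.28 below the median and 0.48 above. This is fair: the intervals are approximate, and a rank test of percentage change is a reasonable companion analysis.
- **Baseline imbalance is weakly supported (P = 0.61), and no secondary conclusion changes.** Both are true. The hemoglobin and VAS results illustrate the method and the loose wording; they do not add to the seriousness of the point.

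**Conclusion.** The concern holds and should be fixed. In the visible text the arms are never compared on change or baseline-adjusted volume, and the statement of similar effects rests on non-significance alone. Under the log-normal assumption with log-SD 0.94, an unadjusted comparison of this size could not exclude volumes 45% lower or 82% higher on one arm even if the observed ratio were exactly 1.0. How much adjustment would narrow that depends on the unreported correlation. Nothing here shows that the treatments differ, or that re-analysis would find a difference; that needs the individual data. The supportable reading of Table 7 is that no difference in final volume was shown.

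**What to change.** 1. Make the between-arm volume analysis an ANCOVA of log 3-month volume on arm and log baseline volume. Report the NAC/dienogest ratio of geometric means with its 95% confidence interval. The smallest volume in Table 7 is 1.00 cm³, so logs are defined.
2. Add a between-arm Mann-Whitney test of each woman's percentage change as a sensitivity analysis. Either analysis closes the mismatch with the sizing; the ANCOVA also gives an interval.
3. Replace the statement of similar effects with one based on that interval.
4. Adjust VAS and hemoglobin for baseline by ANCOVA, and PBAC by rank ANCOVA. In Table 8, either describe P = 0.001 as a test of final score or test improvement directly.
5. Label all of this as specified after the results were seen, and show it beside the existing Table 7 test.

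The cost is revised SAP wording and a short re-analysis of data already collected. The drawbacks are that volume results become ratios and that the analysis is post hoc.
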